### 4.1.5 Analysis Cut-Off Dates

#### 4.1.5.1 Cohort A-C

The primary data cut-off for the analysis will be after 24 weeks after the last subject received M7824.

The final data cut-off will be 1 year after the last subject has received the last dose of M7824.

### 4.1.5.2 Cohort B

The first data cut-off for the interim analysis will be 12 weeks after the  $15^{\text{th}}$  subject enrolled has received study treatment. A decision to continue on to the target 29 patients will be based on the number of responses observed. If 2 or more confirmed responses are observed, the primary data cut-off for the analysis will be 24 weeks after the last subject (n=29) received study treatment.

The final data cut-off will be 1 year after the last subject has received the last dose of M7824.

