### 4.1.2.2 Cohort B – CMS4 mCRC

In this Simon two-stage design, the planned number of subjects is 15 in the first stage. Should at least 2 patients demonstrate radiographic response (i.e. CR + PR), then 14 additional patients will be treated in the second stage, for a total of 29 patients. If there is an anti-tumor signal in the 29 patients with CMS4 metastatic CRC who are treated with this combination, then the study may be amended to expand patient selection across all CMS subgroups.

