## 5.2.2 Radiotherapy (cohort B only)

Radiation therapy will be delivered to a single metastatic lesion, with total dose of 24 Gy in 3 daily fractions of 8 Gy each. Radiation therapy will be delivered on consecutive business days. All 3 fractions will be administered after the second dose of M7824 and prior to the administration of the third dose of M7824.

Patients will undergo CT simulation, with or without IV contrast. The gross tumor volume (GTV) will include a single metastatic lesion. The metastatic lesion to be irradiated must not be adjacent to a dose-limiting normal structure (e.g., heart, bowel) at the discretion of the treating radiation oncologist. The planning target volume (PTV) will include the GTV with a 5-7 mm margin in all directions. For lesions affected by respiratory motion, appropriate motion management techniques should be used, such as inspiratory breathhold. Daily volumetric imaging with cone beam CT (CBCT) or CT on rails (CTOR) will be used for image guidance.

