# 7.1.2 The total sample size of this cohort is 15 patients. With this sample size, the half-width of the 95% confidence interval for the estimated response rate will be at most 0.253. Cohort B

For this cohort, the Simon's Optimum two-stage design will be implemented. A historical response rate of 5% and a target response rate of 25% are assumed under the null and the alternative hypotheses, respectively. In the first stage, we will enroll 15 patients; if 1 or fewer achieves a best response of CR/PR, we will stop enrolling patients. Otherwise, we will continue to enroll all 29 patients and the treatment is deemed as promising if there are 4 or more responders out of these 29 patients. The design has a type I error rate of 0.042, a 90% power and a probability of early termination of 82.9% under the null hypothesis. Patient enrollment will be temporarily suspended when the enrollment for the first stage patients has been completed yet not enough responders have been observed to trigger the start of second stage.

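### Cohort B's stage-1 gate does not settle whether responses must be confirmed, when the 12 weeks start, or what happens to pending confirmations; on one available reading, power falls below the stated 90%

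*Combined protocol and SAP*

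**What the plan says.** Four places bear on the gate.

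- Section 4.1.2.2: "Should at least 2 patients demonstrate radiographic response (i.e. CR + PR"), 14 more patients are treated, for a total of 29. Confirmation is not mentioned.
- Section 7.1.2: "if 1 or fewer achieves a best response of CR/PR, we will stop enrolling patients". Confirmation is not mentioned here either. The hypotheses are set as follows: "A historical response rate of 5% and a target response rate of 25% are assumed under the null and the alternative hypotheses, respectively". The stated properties are type I error 0.042, power 90% and early termination 82.9% under the null. Enrolment is suspended when stage 1 is full "yet not enough responders have been observed to trigger the start of second stage".
- Section 4.1.5.2: "The first data cut-off for the interim analysis will be 12 weeks after the" 15th enrolled subject has received study treatment. Then: "A decision to continue on to the target 29 patients will be based on the number of responses observed". The next sentence sets the timing of the 29-patient analysis and begins: "If 2 or more confirmed responses are observed".
- Sections 6.3 and 7.5.2.1.1: the first asks for every CR or PR to be confirmed under iRECIST 1.1. The second keeps unconfirmed responses out of the final analysis and says nothing about the interim.

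On timing, section 6.1.2 and Table 2 (footnote k) put scans at week 8 and every 8 weeks after that, within 5 days either way. The imaging row also carries footnote q, which allows 7 days. Study treatment in this cohort includes radiotherapy, described in section 5.2.2: "All 3 fractions will be administered after the second dose of M7824 and prior to the administration of the third dose of M7824".

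**The concern.** Cohort B is the only cohort with a hypothesis test. Its stated error rates hold only if all 15 stage-1 patients can be assessed at the gate, on the same endpoint as the final test. The plan does not secure either condition.

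If the gate needs confirmed responses and is read 12 weeks after the 15th patient's first dose, only one scheduled scan falls inside that patient's window. A real responder among the last few patients then counts as a non-responder because the confirming scan is not yet due, and an active regimen can be stopped for that reason alone.

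If the gate does not need confirmation, the gate and the final test use different endpoints. Section 7.1.2 does not say which of them the 5% and 25% describe.

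Whoever applies the gate cannot tell which rule holds. In an open-label trial, the choice could be made with the responses already in view.

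**Working it through.** **Plan's own figures.** Inputs from section 7.1.2: 15 then 14 patients, stop at 1 or fewer, promising at 4 or more of 29, rates 5% and 25%. With X1 ~ Bin(15, p) and X2 ~ Bin(14, p):

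- Early termination = P(X1 ≤ 1) at p = 0.05 = 0.829.
- Rejection probability = Σ over x ≥ 2 of P(X1 = x) × P(X2 ≥ 4 − x) = 0.0418 at p = 0.05 and 0.9001 at p = 0.25.

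All three stated figures reproduce. There is no slack in the 90%.

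**Who cannot be confirmed in time.** Twelve weeks from first dose is day 84. The second scheduled scan is nominally on day 112, on day 107 at the earliest under footnote k, or day 105 if footnote q applies. The gaps are 112 − 84 = 28, 107 − 84 = 23 and 105 − 84 = 21 days. Any patient first dosed fewer than that many days before the 15th has no scheduled confirmation by the cut-off. The 15th patient never does.

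**Effect on a confirmed gate with no waiting.** Let k be the number of such patients, and assume every response is seen at week 8 and later confirmed. The gate is then at least 2 among 15 − k, and the final rule is still at least 4 of 29:

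Σ over x ≥ 2 of P(Bin(15 − k, p) = x) × P(Bin(14 + k, p) ≥ 4 − x).

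| k | False stop at 25% | Power | Type I error |
|---|---|---|---|
| 0 | 8.0% | 90.0% | 0.042 |
| 1 | 10.1% | 88.1% | 0.039 |
| 2 | 12.7% | 85.8% | 0.036 |
| 3 | 15.8% | 82.8% | 0.033 |
| 4 | 19.7% | 79.1% | 0.029 |

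**Size of k.** Accrual for Cohort B is not given, so these rates are assumptions, with even spacing: 1 per month gives k = 1; 2.4 per month gives k = 2 to 3; 4 per month gives k = 3 to 4. The 2.4 is 29 patients over the roughly 12-month window in section 4.1.3 (29 / 12).

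**Clock from the end of radiotherapy.** Radiotherapy starts within 7 days of day 15 of cycle 1 and takes 3 consecutive business days, so the cut-off moves to about day 100 to 109. The gap is then at most 112 − 100 = 12 days, k is 0 to 2 over the same accrual rates, and power is 85.8% to 90.0%.

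**Unconfirmed gate, confirmed final test.** Assume a fraction f of gate responses is later confirmed, with f = 80% (range 70% to 90%; the documents give no figure). The gate uses the unconfirmed rate and the final count uses only confirmed responses.

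| 5% and 25% describe | Early termination at null | Type I error | Power |
|---|---|---|---|
| confirmed response (gate rates 0.05/f and 0.25/f) | 76.0% (70.9–79.9%) | 0.044 (0.045–0.043) | 93.6% (94.7–92.0%) |
| gate response (confirmed rates 0.05f and 0.25f) | 82.9% | 0.021 (0.014–0.031) | 82.2% (74.4–87.2%) |

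The direction of the error therefore depends on which endpoint the rates belong to.

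**The case against.** The strongest answer is that the power loss needs three readings at once: a confirmed gate, a first-dose clock and a decision made without waiting. The last sits badly with section 7.1.2, which holds enrolment until enough responders are seen and sets no deadline. Section 4.1.5.2 is about data cut-offs and never orders a stop at week 12. If the team holds until pending confirmations are in, power stays at 90.0%, provided responses appear by week 8. This stands as a possible reading. But the hold has no stated end, does not mention pending confirmations, and is not reconciled with the fixed cut-off, so it does not remove the other reading.

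It can also be said that silence in sections 4.1.2.2 and 7.1.2 does not waive confirmation, and that section 6.3 supplies it generally. A confirmed definition does fit every section. That resolves the wording in favour of the reading on which the timing problem arises.

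Extra images could help. Section 6.3 considers all available images and lets the investigator add scans. A confirming scan four weeks after week 8 would keep power at 90.0% if all responses appear by week 8. If only 80% do (assumed), power is 89.6% to 86.4% over 0.5 to 4 patients per month. However, extra scans are allowed for medical reasons or suspected progression, and none is planned for confirmation.

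Finally, accrual, response timing and the confirmed fraction are assumptions. That is right. At 1 patient per month the loss is 1.9 points.

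**Conclusion.** The concern holds. The wording gap is unconditional: the gate appears with and without confirmation, the 12-week clock has no defined start, and pending confirmations are not addressed. The stated 0.042, 90% and 82.9% are correct for complete stage-1 data on a single endpoint, which the plan does not guarantee.

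The power shortfall is conditional. With a confirmed gate, a first-dose clock, no waiting and no unscheduled confirming scan, power is at most 88.1% at any accrual rate, and 79.1% with four patients affected. Type I error falls, so the risk is a false stop, not a false claim of activity. Where the gate is unconfirmed, power could be above or below 90%, depending on the endpoint behind the assumed rates. This should be fixed before the gate is applied.

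**What to change.** Use one response definition in sections 4.1.2.2, 4.1.5.2 and 7.1.2, and name the event that starts the 12 weeks.

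If the gate is confirmed, choose one of two rules and, under either, open stage 2 as soon as the second confirmed response is seen:

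- set the stage-1 cut-off after all 15 patients have had the week-16 scan, about 17 weeks (day 119) after the 15th patient's first dose; or
- keep 12 weeks and state that the decision waits for pending confirmations.

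State also that 90% is restored only if responses appear by week 8. If a quarter first appear at week 16 and are confirmed at week 24 (assumed), power at 1, 2.4 and 4 patients per month is 86.9%, 78.8–81.6% and 68.4–73.9% with the 12-week cut-off and no waiting. At 17 weeks it is 89.0%, 87.9% and 86.0–86.7%. The ranges cover scans on the nominal date or 7 days early.

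If the gate is unconfirmed, say so, state which endpoint 5% and 25% refer to, and restate type I error, power and early-termination probability.

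The cost is protocol wording, with no extra scans or patients. The 17-week cut-off adds a pause of up to (119 − 84) / 7 = 5 weeks, and only when fewer than 2 confirmed responses are in hand at week 12. For k = 1 to 4 that is 10–20% of trials at a 25% rate and 85–90% at 5%. Waiting only when pending responses could bring the count to 2 lengthens the pause in 2.1–11.7% of trials at 25% and 1.8–6.9% at 5%, if all pending responses confirm.

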#### 4.1.5.3 Cohort D

The primary data cut-off for the analysis will be after 24 weeks after the last subject received M7824.

The final data cut-off will be 1 year after the last subject has received the last dose of M7824.

### 4.2 Discussion of Trial Design

#### 4.2.1.1 Cohort A-C

This is a Phase Ib, open-label trial in patients with MSI-H metastatic solid tumors who have progressed on prior checkpoint inhibitor treatment.

The study focuses on the subset of patients with metastatic solid tumors that has displayed higher responses rates to immune checkpoint blockade. Microsatellite instability is associated with higher immune infiltration. One early study demonstrated that responders to the anti-PD-1 antibody, pembrolizumab, were restricted to MSI-H mCRC patients in comparison to non-MSI-H CRC. Updated results from this study demonstrated RR of 50% and disease-control rate (DCR) of 89%

seen in MSI-H, compared to 0% and 16% in non-MSI-H mCRC patients, respectively. Pembrolizumab has since received breakthrough designation by the FDA for approval in MSI-H solid tumors (including mCRC). In addition, PD-L1 expression was not associated with OS in this study and preliminary results from the Checkmate-142 trial, in which patients with mCRC were treated with the anti-PD-1 antibody nivolumab. Therefore, using MSI-H as the current selection biomarker for this study is appropriate.

MSI-H non-CRC tumors have demonstrated impressive ORR of 53% with PD-1 blockade in a variety of tumors was 53% and DCR of 77% with median PFS and OS not being met. Given the mechanism of M7824, use of MSI-H as a biomarker as already demonstrated is appropriate to enrich for likely responders while selection based on prior progression following checkpoint immunotherapy approaches ensures targeting of a potential resistance mechanism.

## 4.2.1.2 Cohort B

This is a phase II, single arm, Simon two-stage design to assess efficacy of M7824 as an abscopal phenomenon with radiation to a single metastatic lesion in patients with treatment-refractory, CMS4 mCRC receiving M7824. Tumors  $\geq$  7.0 cm in largest diameter should be excluded from receiving radiation as part of this study. As previously described, TGF $\beta$  represents an immune resistance mechanism via recruitment of immunosuppressive cells and downregulation of existing anti-tumoral responses within the TME. TGF- $\beta$  signaling may also promote resistance to an abscopal phenomenon in patients with mCRC administered immunotherapy with radiation. The trial design is also justified based on pre-clinical evidence that CMS4 mCRC demonstrate an intrinsically inflamed, immunosuppressive phenotype mediated by upregulation of TGF- $\beta$  signaling.

Restriction in this study to CMS4 comes from a number of preclinical studies implicating it with upregulation of TGF- $\beta$  activation. Several of the hallmark features including EMT, stromal infiltration, angiogenesis and matrix remodeling are explained by some of the pleotropic effects of TGF- $\beta$ . TGF $\beta$  represents an immune resistance mechanism via recruitment of immunosuppressive cells and downregulation of existing anti-tumoral responses within the TME. CMS4 is associated with poorer cancer specific outcomes and non-benefit to current adjuvant chemotherapy strategies, and therefore novel effective therapies ae needed for this subpopulation of mCRC.

### 4.2.1.3 Cohort D

This is a pilot study of M7824 in patients with MSS mCRC who have detectable ctDNA following R0 resection of metastatic disease. The inevitability of disease recurrence for patients with colorectal cancer, as seen in the presence of ctDNA following resection of CRC, suggests existence of micrometastatic minimal residual disease in these cases. Given that macroscopic metastases may use TGF- $\beta$  signaling to exclude anti-tumor immune cells from the microenvironment, limiting selection of patients with micrometastatic disease may identify a subpopulation of mCRC patients that selectively benefit from immunotherapy.

# 4.2.2 Inclusion of Special Populations

Not applicable.

## 4.3 Selection of Trial Population

### 4.3.1 Inclusion criteria

- 1. Histologically or cytologically confirmed adenocarcinoma of the colon or the rectum that is metastatic or unresectable (cohort B); or histologically or cytologically confirmed adenocarcinoma of the colon or the rectum following resection of the primary tumor and metastatic disease, following completion of standard-of-care perioperative therapy at the discretion of the treating provider (cohort D).
- 2. Confirmation of:
  - a. Cohort A-C: microsatellite instability
  - b. Cohort B: CMS4 CRC classification on pretreatment primary tumor.
  - c. Cohort D: microsatellite stability
- 3. Age >18 years at time of study entry.
- 4. Ability to provide written informed consent.
- 5. Documented progression to prior therapies (Cohorts A-C and B):
  - a. Cohort A-C: Disease progression following prior immune checkpoint blockade therapy
  - b. Cohort B: Progression or intolerance to at least 2 prior lines of standard therapy for unresectable or metastatic CRC
- 6. Available primary tumor tissue for CMS4 biomarker assessment (cohort B)
- 7. Life expectancy  $\geq 12$  weeks as judged by the treating physician.
- 8. Eastern Cooperative Oncology Group (ECOG) performance status of 0 or 1.
- 9. Measurable disease according to iRECIST v1.1 (Cohorts A-C and B). For cohort B, measureable lesions must be identified apart from the irradiated tumor lesion. Patients in cohort D must have no evidence of radiographically evident disease at the time of study entry.
- 10. Adequate hematological function, defined by ANC  $\geq 1.0 \times 10^{9}$ /L, lymphocyte count  $\geq 0.5 \times 10^{9}$ /L, platelet count  $\geq 100 \times 10^{9}$ /L, and Hgb  $\geq 9$  g/dL (in absence of blood transfusion).
- Adequate hepatic function defined by a total bilirubin level ≤ 1.5 × the upper limit of normal (ULN), an AST level ≤ 2.5 × ULN, and an ALT level ≤ 2.5 × ULN. If liver metastases are present, then it is acceptable for AST level ≤ 5.0 × ULN, and an ALT level ≤ 5.0 × ULN.
- 12. International normalized ratio (INR) < 1.5
- 13. Adequate renal function defined by an estimated creatinine clearance >30 mL/min according to the Cockcroft-Gault formula or be measure for creatinine clearance from 24 hour urine collection.

- 14. **Highly** effective contraception for both male and female subjects if the risk of conception exists. **Highly** effective contraception must be used 30 days prior to first trial administration, for the duration of trial treatment, and at least for 4 months after stopping trial treatment (see Appendix 2 for further details). Should a woman become pregnant or suspect she is pregnant while she or her partner is participating in this trial, the treating physician should be informed immediately.
- 15. Ability to tolerate receipt of radiotherapy to a metastasis not adjacent to a normal doselimiting structure, at the discretion of the treating radiation oncologist (cohort B).
- 16. Presence of detectable ctDNA following completion of R0 resection with or without perioperative therapy (cohort D only).
- 17. Completion of all standard-of-care adjuvant therapy (cohort D).

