aEnrollment will be done after the confirmation of fulfilling all screening inclusion criteria without matching any exclusion criterion. bPhysical examination should include a dermatological examination. If abnormal skin findings are observed, patient should be referred to a dermatologist for biopsy of suspicious lesions. An ophthalmology examination including slit lamp evaluation inclusive of the anterior segment and with visual acuity should be conducted at Screening. At subsequent visits, eye signs and symptoms should be checked. If there are any clinically relevant findings then an appropriate ophthalmology examination including slit lamp evaluation inclusive of the anterior segment and with visual acuity should be obtained within 2 weeks, unless an urgent necessity is determined by the treating provider that requires a sooner evaluation. Starting with C1D15, a focused examination may be performed centered around patient's symptoms at an assigned visit.

°12-lead EKG should be performed as soon after completion of infusion as possible.

dEKGs are to be performed every 6 weeks.

eLaboratory draws may be performed up to 72 hours before a scheduled treatment.

fFor women of child-bearing potential. FSH should be drawn if clarification of post-menopausal state is warranted. Refer to Appendix 2 for further details.

gMandatory fresh tumor biopsies will be collected prior to treatment and prior to dose 2 (i.e., on cycle 1, day 15) and prior to dose 3. An optional tumor biopsy following progression may be offered to the patient.

hMSI testing performed in a CLIA certified laboratory is acceptable and does not need to be repeated (see section 6.4.5)

iCMS on FFPE at CLIA testing laboratory on archival primary tissue or fresh biopsy.

jTumor measurements should occur with CT imaging or MRI. Ideally the same methodology would be used over the course of the study for a given patient. Bone scan should be done at screening if clinically indicated. For collection of those prior imaging studies prior to informed consent, readily available imaging studies since the onset of metastatic/unresectable disease are to be prioritized for collection. If the results of a CT scan or MRI performed within 4 weeks prior to first treatment are available, the screening CT and/or MRI does not need to be performed.

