## 4.3.2 Exclusion criteria

- 1. Concurrent treatment with non-permitted drugs and other interventions.
- 2. Anticancer treatment within 14 days before the start of trial treatment [e.g., cytoreductive therapy, radiotherapy (with the exception of palliative radiotherapy delivered in a normal organ-sparing technique), immune therapy, or cytokine therapy].
- 3. Major surgery as determined by the investigator within 28 days before the start of trial treatment (prior diagnostic biopsy is permitted).
- 4. Systemic therapy with immunosuppressive agents within 7 days before the start of treatment; or use of any investigational drug within 28 days before the start of trial treatment.
- 5. Cohort A-C only: Intolerance or serious adverse immune related adverse events (irAEs) [refer to section 5.5.3.3] that were symptomatic or required or continues to require ongoing immunosuppression to previous immune checkpoint therapy.
- 6. Cohorts B and D: prior exposure to any immune checkpoint blockade agent or any other immunomodulatory agent used for antineoplastic therapy for mCRC.
- 7. Previous malignant disease (other than the target malignancy to be investigated in this trial) within 3 years prior to study treatment initiation. Other Lynch syndrome cancers do not exclude patients from participating on study, at the discretion of the Principal Investigator. Subjects with a history of cervical carcinoma in situ, superficial or non-invasive bladder cancer, or basal cell or squamous cell carcinoma in situ, previously treated with curative intent are NOT excluded. Subjects with other localized malignancies treated with curative intent need to be discussed with the Principal investigator.
- 8. Subjects with active central nervous system (CNS) metastases are excluded. Subjects with a history of treated CNS metastases (by surgery or radiation therapy) are not eligible unless they have fully recovered from treatment, demonstrated no progression for at least 2 months, and do not require continued steroid therapy.
- 9. Receipt of any organ transplantation, including allogeneic stem-cell transplantation, but with the exception of transplants that do not require immunosuppression (e.g., corneal transplant, hair transplant).
- 10. Significant acute or chronic infections including, among others:

- a. Known history of testing positive test for human immunodeficiency virus (HIV) or known acquired immunodeficiency syndrome.

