## 6.4.5 Biomarkers

Due to limited understanding of the biological activities induced by M7824 in cancer subjects, there can be no certainty that the doses examined will be associated with relevant antitumor immune activities. Further details regarding translational studies are listed in Appendix 3. As the consequence, the trial will serve to

- 1. Evaluate MSI-H status with CMS subtype
  - a. MSI will be assessed by MSI-H CRC either by IHC for loss of protein expression in one of 4 mismatch repair proteins (MLH1, MSH2, MSH6, PMS2) or by detection of microsatellites within the tumor DNA (as per institutional practices)
  - b. External MSI testing in a CLIA certified laboratory with a documentation of MSI-H status performed prior to screening is acceptable for inclusion in cohort A- C.
- 2. Evaluate PD-L1 expression as a predictor of response
  - a. Primary tumor will be stained for PD-L1 expression by IHC
  - b. PD-L1 staining will be semi-quantitatively scored by absence, weak, moderate, strong by a pathologist

- c. The above will be performed on the mandatory fresh on-treatment biopsy.
- 3. Evaluate the effect on TGF $\beta$  concentrations in plasma.
- 4. Evaluate potential predictive / prognostic biomarker candidates related to the drug and / or the cancer (such as the CMS, immune infiltrating populations, systemic cytokine profiles)
  - a. CMS will be assessed using a 75 gene FFPE based assay using the Nanostring technology in a CLIA-certified laboratory at MD Anderson.
    - i. Current discovery of 74 samples run in 18 batches with random duplicate samples to assess technical validity demonstrate accuracies compared to gold standard gene expression by Affymetrix hybridization:
      - 1. A 75 gene model had 4 group CMS accuracy of 87.1% with very high accuracies (>90%) in CMS1 and CMS2 groups which were over-represented in this small cohort
      - 2. The CMS4 versus other subgroups demonstrated accuracy of 90.6%
      - 3. The Nanostring technology on FFPE has been successfully applied to breast cancer and lymphoma cohorts
      - 4. The Nanostring codesets utilized for the CMS classification are now being assessed for technical validity in MDA's CLIA molecular pathology laboratory
  - b. Immune infiltrating populations will be analyzed by immunohistochemistry (IHC), and Multiplex IF analyses.

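### Cohort B relies on the CMS4 label alone to keep MSI-H patients out, so its 5% null response rate is unprotected although an MSI test is already scheduled at screening

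*Combined protocol and SAP*

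**What the plan says.** - **Section 4.3.1, criterion 2.** Cohort A-C needs microsatellite instability. Cohort D has "Cohort D: microsatellite stability". Cohort B has only "Cohort B: CMS4 CRC classification on pretreatment primary tumor". Neither the exclusion criteria (4.3.2) nor the Cohort B pre-screening criteria (4.3.3) mention MSI status.
- **Table 2 (Cohort B schedule).** MSI testing is marked at screening. Footnote h adds that "MSI testing performed in a CLIA certified laboratory is acceptable and does not need to be repeated". No eligibility consequence is attached. Section 6.4.5 links external MSI documentation to inclusion for Cohort A-C only.
- **Section 4.3.2, exclusion 6.** It removes "Cohorts B and D: prior exposure to any immune checkpoint blockade agent". Criterion 5b adds "Cohort B: Progression or intolerance to at least 2 prior lines of standard therapy for unresectable or metastatic CRC".
- **Section 7.1.2, Cohort B.** "A historical response rate of 5% and a target response rate of 25% are assumed under the null and the alternative hypotheses, respectively". Enrolment stops if 1 or fewer of 15 respond, and the treatment is promising if 4 or more of 29 respond. The stated type I error is 0.042, power 90% and early termination under the null 82.9%.
- **Response of MSI-H disease.** Section 2.2.6.7 gives 31% and 50% for single-agent treatment of MSI-H mCRC. Section 4.2.1.1 gives 50% in MSI-H against 0% in non-MSI-H mCRC.
- **Link between MSI and CMS.** Section 2.2.5 describes MSI-H as a subset of CMS1. Section 6.4.5 reports, from 74 discovery samples, "The CMS4 versus other subgroups demonstrated accuracy of 90.6"%, with CMS1 and CMS2 accuracies above 90%. It says the codesets are still being assessed for technical validity.

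**The concern.** Cohort B asks whether radiotherapy makes M7824 active in a subtype where M7824 alone did little (sections 2.2.5 and 2.2.6.7). An MSI-H, checkpoint-naive patient may respond to the PD-L1 component by itself, and such a response does not bear on that question. Followed to the letter, the plan would admit this patient with the MSI result already on file.

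The decision rests on very small counts. One such responder is half of the 2 responses needed to pass stage 1 and a quarter of the 4 needed at the end. Section 4.1.2.2 also says that a signal may lead to expansion across all CMS subgroups, which would include CMS1, where the protocol places MSI-H.

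**Working it through.** **Inputs from the documents.** n1 = 15, stop if 1 or fewer respond; n = 29, promising if 4 or more respond; p0 = 0.05, p1 = 0.25 (section 7.1.2). MSI-H response rate m = 0.31 and 0.50 (sections 2.2.6.7 and 4.2.1.1).

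**Assumptions.** M7824 acts in checkpoint-naive MSI-H mCRC like the quoted anti-PD-1 agents; the documents give no M7824 rate there. The MSI-H share q among patients called CMS4 is not in the documents, so it is varied.

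**Step 1: the plan's own figures.** With X1 ~ Bin(15, p) and X2 ~ Bin(14, p):

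P(promising) = sum over x ≥ 2 of P(X1 = x) × P(X2 ≥ 4 − x)

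- p = 0.05: early termination = 0.4633 + 0.3658 = 0.829; P(promising) = 0.0418.
- p = 0.25: P(promising) = 0.900.

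All three stated figures reproduce.

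**Step 2: exactly one MSI-H patient in stage 1, all others at 5%.** Among the 14 other stage-1 patients, P(0 responses) = 0.4877 and P(1) = 0.3593, which sum to 0.8470. Early termination = (1 − m) × 0.8470 + m × 0.4877:

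- m = 0.31: 0.69 × 0.8470 + 0.31 × 0.4877 = 0.736
- m = 0.50: 0.50 × 0.8470 + 0.50 × 0.4877 = 0.667

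The chance of passing stage 1 therefore rises from 0.171 to 0.264-0.333. Putting the mixed stage-1 distribution into the step 1 formula gives:

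| MSI-H patients | P(promising), m = 0.31 | P(promising), m = 0.50 |
|---|---|---|
| none | 0.042 | 0.042 |
| one in stage 1 | 0.071 | 0.092 |
| one in stage 2 only | 0.058 | 0.070 |
| one in each stage | 0.096 | 0.147 |

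**Step 3: an assumed share q instead of a fixed count.** The average rate is p = (1 − q) × 0.05 + q × m, put into the step 1 formula. The last column is 1 − (1 − q)^29.

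| q (assumed) | P(promising), m = 0.31 | P(promising), m = 0.50 | P(at least one MSI-H in 29) |
|---|---|---|---|
| 0% | 0.042 | 0.042 | 0 |
| 0.5% | 0.045 | 0.048 | 0.14 |
| 1% | 0.049 | 0.054 | 0.25 |
| 2% | 0.056 | 0.069 | 0.44 |
| 5% | 0.083 | 0.121 | 0.77 |

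**Step 4: sensitivity to the rate in the other patients.** One MSI-H patient in stage 1, as in step 2, with the others at a rate below 5%:

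| Rate in others | No MSI-H patient | One in stage 1 (m = 0.31 to 0.50) |
|---|---|---|
| 0% | 0 | 0 |
| 2% | 0.002 | 0.006-0.009 |
| 3% | 0.008 | 0.019-0.026 |
| 4% | 0.021 | 0.040-0.054 |
| 5% | 0.042 | 0.071-0.092 |

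One MSI-H patient raises the probability in every row with a background above zero. It exceeds the stated 0.042 only when the other patients are near 5%.

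**The case against.** The strongest reply is that CMS4 selection already excludes MSI-H. If MSI-H lies within CMS1, a correctly classified CMS4 tumor is not MSI-H, and the relevant error is CMS1 called CMS4, in a class where the assay is reported above 90% accurate. The patient must also have had two standard lines and no checkpoint inhibitor. The investigator will have the MSI result in hand and could decline to enrol. One MSI-H responder cannot meet either threshold alone.

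Most of this stands, and it makes the expected number small. It does not make it zero: the protection runs through a classifier whose technical assessment is unfinished, while the direct test is scheduled and has no stated use. Exploratory objective 4 plans to correlate MSI with CMS1, which is a routine correlation and not evidence that MSI-H occurs in CMS4.

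Two stronger readings are tempting, and the documents support neither:

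- **A reader might infer that the 5% null is broken.** It fails only if an MSI-H patient actually enters, and nothing in the documents shows that one has or will.
- **A reader might take the remaining 9.4% (100 − 90.6) as the rate at which MSI-H patients slip through.** That figure pools errors in both directions and across all the other subtypes, so it is not a leakage rate.

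The choice of background rate is also a fair challenge. Section 4.2.1.1 quotes 0% response in non-MSI-H disease, and at that rate one MSI-H patient changes nothing. Against this, 5% is the design's own null, and section 2.2.5 reports 1 response among 10 CMS4 patients on M7824 alone.

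**Conclusion.** The gap in the text is certain: no rule keeps an MSI-H, checkpoint-naive patient out of Cohort B, so the null rate is unprotected. The size of the effect is conditional. One MSI-H patient in stage 1 would move the false-positive probability from 0.042 to 0.071-0.092. With an assumed 1% to 2% share it would be 0.049-0.069, and at 0% there is no effect. These figures rest on anti-PD-1 response rates borrowed for M7824, an MSI-H share the documents do not give, and other patients responding near 5%. The stated operating characteristics are correct. This is an inexpensive improvement to a decision that turns on 2 and 4 responders; it does not show the design to be invalid.

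**What to change.** Extend criterion 2b to require CMS4 classification on the pretreatment primary tumor **and** microsatellite stability (not MSI-H or mismatch-repair deficient), using the MSI test already in Table 2 with the result available before enrolment. If an MSI-H patient has already been enrolled in Cohort B, report the 2-of-15 and 4-of-29 decision counts with and without that patient.

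The cost is one line of eligibility wording and the loss of a very small number of otherwise eligible patients. No new test is needed, and the sample size, thresholds and stated operating characteristics stay as they are.
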